**RISKS TO PARTICIPANTS:**

Potential risks of participating in the proposed research:

1. Sleep deprivation - The risks associated with acute sleep deprivation in the study will be similar to risks experienced with habitual sleep deprivation. Some participants may feel fatigued, sluggish, irritable, and may complain of lack of energy and concentration on the day following study induced sleep deprivation. To mitigate these risks, participants will be advised to get adequate recovery sleep during the week following the study procedure. Participants will also be advised to refrain from driving and using heavy machinery on the day following the sleep deprivation.

2. Blood draw - Participants may feel bruising or bleeding at the site of venipuncture. Venipuncture will be performed by the trained nursing staff at the Clinical Research Unit. This should reduce the chance of pain, discomfort, and bruising during the blood draws.
3. Functional Magnetic Resonance imaging (fMRI) - There are no known risks associated with undergoing fMRI scanning. All fast imaging sequences (those provided by Siemens Medical Systems or those developed at Northwestern) are monitored by safety devices built into the MR scanner to ensure that pulse sequences perform within FDA guidelines for human safety. Of major concern is the specific absorption rate (SAR) of radiofrequency energy used in generating an image. This value is physically measured and calculated three different ways. The largest value is used in determining if that particular scan is safe to use. This method and its implementation are currently FDA approved. There is no way to override this safety feature on our scanner.

During fMRI scanning, some subjects report discomfort from having to lie still in the scanner for a long period of time, and some subjects feel anxious or claustrophobic in the scanner. Highly trained staff members will be working with the subjects throughout the study and will take appropriate steps to minimize anxiety and fatigue. Although smelling the odors should not present any significant health risks, it is possible that a subject could have an allergic reaction. For this reason, any subject with a history of serious food or non-food allergies, or a history of asthma requiring hospitalization, will be unable to participate in the study. Additionally, subjects may be asked to refrain from eating for 6 hours prior to participation in the experiment. Some subjects may experience dizziness due to fasting

If an abnormal finding is seen on the anatomical MRI scan, the PI will contact the subject and recommend a clinical evaluation. Copies of the abnormal scan will be sent to the patient's physician upon request.

4. Olfactory stimulation- Although smelling the odors should not present any significant health risk, it is possible that a subject could have an allergic reaction. Therefore, subjects with a history of serious food or non-food allergies, or a history of asthma requiring hospitalization, will be excluded from the study. Selected odorants will be presented at concentrations and durations that have been safely used in prior olfactory experiments and should not present any health risks to the subjects. Stimulus parameters will be adjusted to ensure that the exposure limits, where indicated on the odorant material data safety sheets, are not exceeded.
5. Privacy and Confidentiality- To preserve subject privacy and confidentiality, all research materials (questionnaires, behavioral testing results, and magnetic resonance imaging data) will be coded by a different study code number unique for each subject, in order to keep the identity and personal information of each subject as confidential as possible. This number will be recorded on all testing sheets instead of the subject's name. In addition, if the individual results of this study are used for teaching, research, publications, or presentations at scientific meetings, subject identity will be protected by using the study code number rather than subject name or other identifying information, including (but not limited to) Social Security number, date of birth, or address. Finally, unless required by law, only the study investigator, members of the investigator's staff, representatives from the Cognitive Neurology and Alzheimer's Disease Center, and the Northwestern University Institutional Review Board will have the authority to review the study records. They will all be required to maintain the strictest confidentiality regarding subject identity.

**POTENTIAL BENEFITS TO PARTICIPANTS:**

There are no direct benefits of participation in the study.

**VULNERABLE POPULATIONS:**

STU#:00203395

N/A

**COMMUNITY-BASED PARTICIPATORY RESEARCH:**

N/A

**SHARING OF RESULTS WITH PARTICIPANTS:**

If requested by the participant, study results may be shared with the participant. We are not performing any diagnostic procedures in the study, therefore will not be able to identify any abnormalities. However, if an abnormal finding is seen on the anatomical MRI scan, the PI will contact the subject and recommend a clinical evaluation. In this case, copies of the abnormal scan will be sent to the patient's physician upon request.

**SETTING:**

Prior to recruitment in the study, consent and screening process will be performed at our lab at the Department of Neurology. Once deemed eligible to participate in the study, participants will be instructed to follow a one-week sleep stabilization period at home. After a week subjects will spend a night either sleep deprived (SD, 4 h of sleep) or with normal sleep (non-SD, NDS, 8 h of sleep) at home. On the next day, fMRI scanning will be conducted and blood samples will be collected at the Center for Translational Imaging (CTI), Northwestern University.

**RESOURCES AVAILABLE:**

Our lab has conducted multiple studies and published manuscripts in the area of neural imaging of olfaction and reward regions in high impact peer reviewed journals. This study will combine our expertise in neural reward processing, olfactory psychophysics, and food-related choices in obesity to address the posed research question. All research personnel involved in the study have extensive experience in conducting all aspects of research study including consent, screening, recruitment, and use of olfactometer and scanner. Some members of the study team are also certified to conduct the fMRI in the CTI independent of the CTI staff. In addition, the primary researcher of this project also has previously worked with the Clinical Research Unit at a different institution and has extensive knowledge of the process involved. Overall, all research personnel involved in the study are well equipped to conduct the study.

We have access to several research related resources to successfully conduct this study. We have a custom built olfactometer in the lab that will be used to deliver odors both outside and inside the scanner. The other sites where the study will be conducted (CTI) are also within walking distance from our lab. The screening and the olfactometer behavioral tasks will be conducted in a quiet ventilated room in our lab, accessible only by the research personnel. Brain imaging will be performed at the CTI using the state-of-the-art 3T Prisma platform by a certified and MRI safety trained study personnel. On the day of the scan, subjects will fill out the safety form prior to the scan. The form will be submitted to the MR tech to verify subject safety. In addition, two safety-trained study team members will be present for all human scans. In case of emergency CTI staff will be present to assist the study team. The primary researchers on the project will contribute 100% of her time on the project. Other staff involved in the study is expected to contribute 20-25% of their time on the project.

Meetings will be conducted with the CRU team to discuss the protocol and procedure flow chart will be developed to ensure that the mobile nurse assisting with the research is adequately informed about the protocol and the research procedures.

**PRIOR APPROVALS:**

N/A

**RECRUITMENT METHODS:**

Subjects will be recruited from flyers posted around Northwestern, DePaul, and Loyola University, or by email. Interested subjects will contact the PI or a research assistant at a phone number or by email indicated on the flyer. During this initial conversation, the PI or research assistant will email an online questionnaire through Google Forms that is completed by the interested subjects; this is used for screening subjects for inclusion and exclusion criteria. If they meet these initial study criteria, subjects will review and sign (either electronically or manually) an Informed Consent form for participation in the study. The subject will also review and sign an MRI-specific safety form. A copy of all consent forms will be provided to the subject; if signed electronically, a printed form will be provided. Subjects will be paid a total of \$240 for participation in the complete study. If the subject is only able to complete a portion of the study, monetary compensation will be prorated on the basis of procedures completed. The 90 minute fMRI scanning procedure will also be prorated independently in both the sleep deprived and non-sleep deprived stages. Subjects will receive all payment in the form of a check (or in the case of a Northwestern University employee, direct deposit) at the completion of participation in the study, and payment may be subject to tax withholding.

The recruitment process will encourage the participation of women through widespread flyers aimed at the students and staff of Northwestern University. Based on subject recruitment patterns through the Department of Neurology over the last 3 years, we expect equal numbers of men and women to participate in the studies.

Similarly, the recruitment process will encourage the participation of minorities through flyers aimed at the students and staff of Northwestern University that have a wide readership. Recent recruitment patterns achieved at the Department of Neurology reflect a diverse ethnic assortment of subjects.

**NUMBER OF LOCAL PARTICIPANTS:**

A total of 40 participants will be enrolled locally. This allows for the possibility of excluding subjects from analysis due to failure to comply with the sleep protocol, claustrophobia, technical issues, or other unanticipated situations which may arise during MRI scanning. We expect a drop-out rate of 15-25%.

**CONFIDENTIALITY:**

This is not a multicenter study therefore this section is not applicable.

**PROVISIONS TO PROTECT THE PRIVACY INTERESTS OF PARTICIPANTS:**

To ensure subject privacy, no data collection will occur in a group setting or in public. Study personnel will keep participation and results confidential by using code numbers to identify subjects on all reports and samples. Only the mobile CRU nurse will have access to the patients' medical records

Potential psychosocial risks to subjects are that some of the questions asked may be upsetting or may make the subject feel uncomfortable. Some participants may also find these questionnaires frustrating and time consuming. There may also be a potential risk of loss of confidentiality. To minimize the risks associated with loss of confidentiality, strict measures will be taken as detailed elsewhere in the application. In particular, participants will be given the option to skip certain questions if they do not feel comfortable answering them. However, if that question is part of inclusion/exclusion criteria, the prospective participant may not participate in the study to maintain the purpose of the study. Study staff will not have access to the medical records of the participants.

**COMPENSATION FOR RESEARCH-RELATED INJURY:**

This research does not involve more than minimal risk.

**ECONOMIC BURDEN TO PARTICIPANTS:**

Participants will not be responsible for any cost related to the participation in the study.

**CONSENT PROCESS:**

All subjects will provide their written informed consent at the screening visit. The consent process will take place in our lab at the Department of Neurology, Feinberg School of Medicine. Information on the purpose of the study and routine potential risks associated with the study procedures will be provided to the potential subjects by the research personnel. All risks, costs, and benefits will be discussed. All potential participants will be given time to ask questions and make the decision on whether they would like to participate in the study. Subjects will be assured of their right to withdraw at any time without prejudice to their care. They will also be assured of confidentiality in maintaining records and reporting of results. Written informed consent will be obtained before entry into the study form all participants. Subjects will also review and sign an MRI-specific safety form. A copy of all consent forms will be provided to all subjects. To minimize possibility of coercion, participants will be given a choice to have a digital version of the consent form with all study information sent to them prior to the screening visit. Participants will be given one week to decide if they want to participate in the study. They will also be given a copy of the consent form if they want to read it again.

***For Non-English Speaking Participants***

Non-English speakers will not be included in the study.

***Waiver or Alteration of Consent Process***

N/A

***Participants who are not yet adults (infants, children, teenagers)***

N/A

***Cognitively Impaired Adults***

N/A

***Adults Unable to Consent***

N/A

**PROCESS TO DOCUMENT CONSENT IN WRITING:**

We will document consent in writing. The consent form is attached to the eIRB application.

**DRUGS OR DEVICES:**

N/A

## fMRI data pre-processing

Pre-processing of fMRI data was performed using SPM12 (<http://www.fil.ion.ucl.ac.uk/spm/software/spm12/>). For each participant, we aligned all functional volumes for both sleep sessions to the first acquired functional volume to correct for head motion. We then realigned and averaged the ten whole-brain EPI volumes, and co-registered the mean whole-brain EPI to the anatomical T1 image. The mean functional volume was then co-registered to the mean whole-brain EPI, and this transformation was applied to all functional volumes. Spatial normalization was performed by normalizing the T1 anatomical images to the MNI (Montreal Neurological Institute) space using the six tissue probability map provided by SPM12. For multivariate analysis, the resulting deformation fields were applied to searchlight-based maps of decoding accuracy (see below). The normalized decoding accuracy maps were spatially smoothed with a 6 x 6 x 6 mm full-width half-maximum (FWHM) Gaussian kernel before group-level statistical testing. For functional connectivity and univariate analyses (see below), the motion-corrected and co-registered functional images were normalized to MNI space using the previously estimated deformation fields and spatially smoothed with a 6 x 6 x 6 mm FWHM Gaussian kernel.

## Multivoxel pattern analysis

We implemented a searchlight-based multi-voxel pattern analysis (MVPA) (Howard & Kahnt, 2018; Kahnt, Grueschow, Speck, & Haynes, 2011) to decode information about food vs. non-food odors. We first estimated general linear models (GLM) for each subject, separately for each session, using the non-normalized and un-smoothed functional images. The GLM included three regressors of interest specifying onset times for the following conditions: 1) food odors, 2) non-food odors, 3) clean air. We also included the following nuisance regressors: the smoothed and normalized respiratory trace, down-sampled to scanner temporal resolution (0.5 Hz); the 6 realignment parameters (3 translations, 3 rotations), calculated for each volume during motion correction; the derivate, square, and the square of the derivative of each realignment regressor; the absolute signal difference between even and odd slices, and the variance across slices in each functional volume (to account for fMRI signal fluctuation caused by within-volume head motion); additional regressors as needed to model out individual volumes in which particularly strong head motion occurred (absolute difference between odd and even slices >5 SD or slice variance >4 SD). The parameter estimates from the first two regressors of this GLM reflect the voxel-wise response amplitudes for food and non-food odors, separately for each run and sleep session.

Next, we used these voxel-wise parameter estimates in a searchlight-based, leave-one-run-out cross-validated decoding approach. We decoded food vs. non-food odors from patterns of odor-evoked activity, separately for each of the two sleep sessions. We used The Decoding Toolbox (TDT) to implement the searchlight (Hebart, Gorgen, & Haynes, 2014) and LIBSVM (Chang & Lin, 2011) for the linear support vector machine (SVM) classifier. To test for brain regions that encoded food vs. non-food odors, at each searchlight (sphere with 8 mm radius), we trained a SVM to discriminate between activity patterns evoked by food vs. non-food odors in three of the four runs per session (DS or NDS), and tested it on activity patterns evoked by food vs. non-food from the fourth “left out” run of the same session. The procedure was repeated four times leaving a different run out, and decoding accuracies were averaged and mapped to the center voxel of the searchlight. This procedure was repeated for every voxel within a 10% gray-matter mask (based on SPMs tissue probability map that was inverse-normalized into the individual native space, as described in (Howard & Kahnt, 2018)). The resulting accuracy maps for food vs. non-food odors for DS and NDS sessions were subtracted (DS > NDS), normalized, and smoothed (6mm FWHM). We tested for significant differences between DS and NDS sessions at the group level using voxel-wise one-sample t-tests. Statistical thresholds were set to  $P < 0.05$ , family-wise error (FWE)

small-volume corrected for multiple comparisons at the voxel-level in a functional mask of piriform cortex that was obtained from a one-sample t-test of decoding accuracy for food vs. non-food odors, averaged across sleep sessions.

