**MULTI-SITE RESEARCH: N/A**

**STUDY TIMELINES:**

Each participant will follow a ~ 6 week within-subject, crossover partial sleep-deprivation protocol to test the effect of sleep deprivation (SD) and non-sleep deprivation (NSD) on neural processing of food odors in sensory and reward related regions (**Fig. 2**). Qualified subjects will be randomly assigned to either participate in the SD or the NSD condition first. Subjects will then undergo a week of sleep stabilization phase to stabilize circadian rhythms for a week. After the sleep stabilization week, the night before the fMRI session, subjects will either sleep normally (NSD, 8 h of sleep between 11 pm and 7 am), or sleep only for 4 h between 1 am and 5 am (SD) at home. All subjects will participate in both sleep conditions (SD and NSD) in randomized order, separated by ~2.5 week washout period. The

evening of the sleep manipulation, subjects will visit the lab to consume dinner and pick up their sleep monitors. We will also provide a take-out breakfast and lunch to be consumed at 8:00 am and 12 noon, respectively. All meals will be provided by the CRU. Subjects will perform an odor-rating task inside the MRI scanner on the same evening. Serial blood samples will be collected for measurement of appetite-regulating hormones. At the completion of the fMRI scan, participants will be provided with snacks in a buffet-style setting where they will have *ad libitum* access to food items corresponding to the odors used during fMRI scanning (sweet and savory high-calorie snacks). They will be instructed to consume as much food as they like. We anticipate to enroll all participants within a 12-month period and plan to complete the study data collection and analyses within a period of 3 years from the date of IRB approval.

**Figure 2. Study design and scanning protocol. A.** Timeline of the sleep-deprivation protocol. All subjects will participate in both sleep conditions (SD and ND), in randomized order. On the scanning day, blood (BD) will be drawn every 30 min. **B.** For each subject, two sweet and two savory high-calorie food odors will be selected and presented during the scanning session, in addition to two non-food odors and trials in which non-odorized air is presented. **C.** Example trial of the fMRI task. After a countdown, an odor is presented, after which subjects have to rate the pleasantness or the intensity of the delivered odor.

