*fMRI scanning protocol.* On the first day of the study, before being assigned to the SD or NSD phase, subjects will rate the pleasantness of six food odors, including three high caloric sweet (caramel, yellow cake, ginger bread) and three high caloric savory odors (potato chips, pot roast, garlic butter). Based on each participant's ratings, we will select two sweet and two savory odors matched in rated pleasantness. We will also include two control non-food odors (fir and celery seed). On the day of fMRI scanning, subjects will arrive at the imaging center at 6 pm and will consume a dinner before entering the scanner. This pre-feeding will satisfy metabolic hunger (i.e., energy requirements), and thus render the fMRI measures more sensitive to sleep-dependent changes in hedonic hunger, i.e., food intake exceeding energy requirements (47). During fMRI data acquisition, odors will be delivered directly to the subject's nose via a MR-compatible olfactometer. Neuroimaging will be performed at the Northwestern University Center for Translational Imaging (CTI) on a state-of-the-art Siemens PRISMA system with a 64 channel head coil, using imaging sequences optimized for signal recovery in olfactory and orbitofrontal cortices (48). Specifically, subjects will perform 4 runs of an odor detection task inside the MRI scanner while blood oxygen-level dependent (BOLD) responses will be acquired with high spatial (2 mm isotropic) and temporal resolution (2000 ms). On each trial, subjects will be cued to sniff, and an odor corresponding to one of the three experimental groups (sweet, savory, non-food) or clean air will be delivered pseudo-randomly. Subsequently, subjects will rate the pleasantness or the intensity (pseudo-randomized) of the delivered odor. Sniffing behavior will be monitored using an MR-compatible breathing belt and a spirometer. A high-resolution anatomical image will be acquired for the purpose of spatial normalization and anatomical localization of the fMRI responses.

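### If food odors were given about twice as many trials as non-food odors, the pooled food regressor biases food vs non-food decoding above 50% and can distort the piriform mask; the DS minus NDS test keeps its type I error

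*SAP*

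**What the plan says.** The protocol (Study Timelines, Figure 2 legend) says of every participant that "two sweet and two savory high-calorie food odors will be selected and presented during the scanning session, in addition to two non-food odors", plus clean-air trials. Under Procedures Involved (fMRI scanning protocol), on each trial "an odor corresponding to one of the three experimental groups (sweet, savory, non-food) or clean air will be delivered pseudo-randomly". Neither document says how many trials each odor, group or run receives.

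The SAP (Multivoxel pattern analysis) merges sweet and savory into one regressor, so that the regressors of interest are "1) food odors, 2) non-food odors, 3) clean air". The first two give "voxel-wise response amplitudes for food and non-food odors, separately for each run and sleep session". A linear SVM is trained on three of a session's four runs and tested on the fourth, in a searchlight ("sphere with 8 mm radius"). Two group-level uses follow:

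- The DS and NDS accuracy maps are subtracted, and the difference is tested with a one-sample t-test.
- That test is small-volume corrected in a "functional mask of piriform cortex that was obtained from a one-sample t-test of decoding accuracy for food vs. non-food odors", with accuracy averaged over the two sessions.

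No matching or subsampling of trials is described. The reference value and threshold of the mask test are not stated.

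**The concern.** Two natural readings of the design give the same ratio. With k trials per odor, food has 4k and non-food 2k. With k trials per group, food (sweet plus savory) has 2k and non-food k. Both are 2:1. Only presenting each non-food odor twice as often as each food odor would give 1:1, and neither document says this was done.

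At 2:1, the food estimate in each run averages more trials and is less noisy. A linear SVM trained on three quiet and three noisy patterns tends to place its boundary on the noisy side, so most test patterns are called 'food'. The gain on food patterns slightly exceeds the loss on non-food patterns, and mean accuracy exceeds 50% with no true pattern difference. Voxels could then enter the piriform mask, or be reported as encoding food vs non-food, because of trial counts alone.

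**Working it through.** The documents state no expected accuracy or trial count, so there is no planned figure to reproduce. The check is a simulation of the described pipeline with identical true patterns in both classes.

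**Inputs from the documents.** Four runs per session; one estimate per condition per run, so training is 3 vs 3 and testing 1 vs 1; two sessions; 8 mm radius at 2 mm voxels, which is 257 voxels; 40 enrolled with 15-25% drop-out, so 40 × 0.75 = 30 to 40 × 0.85 = 34 analysed (40 is also shown).

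**Assumptions.** Trials 2:1. Non-food trial-noise variance 1, hence food 1/2. Extra run-to-run variance v that does not fall with trial count, equal in both classes: 0, 1 or 3. Spatial correlation FWHM 0, 4 or 8 mm. Linear SVM with C = 1. Group tests one-sided at 0.05, with the mask-type test taken against 50%. Each setting uses 8,000 simulated subjects.

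**Variance ratio.** Food/non-food = (0.5 + v)/(1 + v): 0.50 at v = 0, 1.5/2 = 0.75 at v = 1, 3.5/4 = 0.875 at v = 3. The asymmetry fades as v grows.

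**Null results.** Rejection rates are for a single voxel at n = 30 / 34 / 40.

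| FWHM | v | Accuracy | P(call 'food') | Averaged accuracy vs 50% | DS minus NDS vs 0 |
|---|---|---|---|---|---|
| 0 mm | 0 | 51.5% | 0.98 | 69 / 74 / 80% | 4.6 / 3.5 / 4.1% |
| 4 mm | 0 | 53.6% | 0.79 | 51 / 53 / 61% | 5.7 / 5.2 / 4.8% |
| 8 mm | 0 | 52.4% | 0.66 | 24 / 25 / 27% | 6.6 / 6.4 / 7.0% |
| 0-8 mm | 1 | 50.3-51.6% | 0.56-0.80 | 6-22% | 4.2-6.1% |
| 0-8 mm | 3 | 49.9-50.5% | 0.53-0.66 | 4-9% | 4.4-5.5% |
| 0-8 mm, equal trials | 0 | 50.0-50.2% | 0.50 | 5-6% | 5-6% |

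**Per-class rates.** Let f and g be the proportions of food and non-food patterns labelled correctly. Accuracy = (f + g)/2 and P(call 'food') = (f + 1 − g)/2. At 0 mm, v = 0: f + g = 1.030 and f − g = 0.952, so f = 0.99 and g = 0.04. At 4 mm: 1.072 and 0.570, so f = 0.82 and g = 0.25.

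**Why a small bias can reject so often.** When nearly everything is called 'food', accuracy hardly varies between subjects. At 0 mm its SD is 0.038, so at n = 34 the expected t is 0.0148/(0.038/√34) = 2.27, against a critical value of 1.69. At 8 mm the SD is 0.139 and the expected t is 0.0241/(0.139/√34) = 1.01. These agree with rejection of 74% and 25%.

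**Robustness.** At 4 mm and v = 0, changing C from 0.001 to 100 left accuracy at 53.1-53.6%. A hard-margin version with 10, 30, 60, 120 and 257 independent dimensions gave null accuracy of 52.0, 52.6, 53.1, 53.3 and 51.5%, with rejection at n = 32 of 20, 32, 47, 81 and 75%.

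**DS minus NDS.** Both sessions come from the same distribution, so the true difference is zero. The 7.0% at 8 mm belongs to a simulated pool whose mean difference was 0.7 points by chance (SE = 2 × 0.139/√8000 = 0.3 points). Making DS noisier (noise SD × 1.5, or trial variance × 2 with run variance fixed) moved the difference by 0.0-0.1 points (SE 0.3).

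**Sensitivity of DS minus NDS.** In one set of alternatives with trial noise only, power at 257 dimensions was 0.13 pooled against 0.23 with balanced trials. At 30 dimensions there was no loss.

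**The case against.** A reader might infer that the decoding test itself is corrupted. The documents do not support that. The group comparison in the SAP is a within-subject subtraction of two accuracy maps. The food odors are chosen once, from ratings taken before assignment, so the same imbalance should apply in both sessions and the bias cancels. Nor does the mask favour DS: it uses the session average, and extra uninformative voxels enlarge the search volume, which makes the FWE correction stricter.

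A reader might also infer that the classifier has unequal class sizes. It does not: it receives one pattern per class per run. The only route is unequal noise in those patterns.

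The remaining objections concern size, and they stand. The 2:1 ratio is inferred. The highest rejection rates need trial noise to dominate and many independent dimensions, which 257 neighbouring 2 mm voxels are unlikely to provide. The rates are single-voxel and uncorrected against an assumed 50%; they are not error rates of the SAP's mask procedure, whose threshold is not given. With run-to-run variance at three times the trial noise, rejection is close to nominal. The documents do not show which case applies. None of this removes the bias where trials are 2:1 and trial noise is substantial.

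**Conclusion.** The concern holds conditionally. If odors or odor groups are equally frequent, the food estimates are less noisy and the classifier leans towards 'food'. Session-averaged accuracy with no true pattern difference then exceeds 50% by about 1.5-3.6 points when trial noise dominates, with single-voxel rejection of about 20-80% against a nominal 5%. Rejection is 6-22% when run-to-run variance equals the non-food trial noise, and 4-9% when it is three times that. What is exposed is the functional piriform mask and any claim that a region decodes food vs non-food above chance.

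The type I error of the DS minus NDS test stays near 5%, provided trial counts are the same in both sessions. There the only cost is possible loss of sensitivity, from a larger search volume and from a classifier that mostly gives one answer. This is a cheap and worthwhile correction, not a flaw that invalidates the sleep comparison.

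**What to change.** State in the SAP the number of trials per regressor per run, in each session. If food and non-food counts differ, equalise them before decoding by one of two routes:

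- Subsample food trials to the non-food count, repeat over several draws and average the accuracies. This keeps the planned food vs non-food classifier.
- Model sweet and savory as separate regressors, decode each against non-food, and average the two accuracies before averaging or subtracting sessions. This suits the case where sweet, savory and non-food have equal counts, and it changes what each classifier decodes.

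Build the piriform mask from the balanced accuracy, state its reference value and threshold, and report the food-correct and non-food-correct rates separately, since they show any residual lean at once.

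A label-permutation null is not a substitute. Permuting labels within runs on unequal-variance null data gave a permutation mean of 50.0% at 30, 120 and 257 dimensions, while the unpermuted null means were 53.1, 53.1 and 51.6%. Permutation mixes the variances and leaves the bias in place.

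The cost is SAP wording and one rerun of the decoding on existing data, with a slightly noisier food estimate. If the counts prove equal, stating them is enough.
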